The sample size was estimated to ensure sufficient power to compare the prevalence of major congenital malformations in the infants of women exposed to OUVIVIO (Cohort A) to infants of women exposed to other non-ORA medications for insomnia (Cohort B1) in the primary analysis using a non-inferiority testing approach. Assuming exposure in the first trimester of pregnancy, a general population prevalence of major congenital malformations of 3% among women in Cohort B1, and an expected prevalence of major congenital malformations of 3.15% among women in Cohort A, an estimated 102 pregnancy outcomes in Cohort A and 204 in Cohort B1 (1:2 ratio) would provide 80% power to rule out a difference represented by a risk ratio of 3.0 or higher in major congenital malformations at a one-sided significance level of $\alpha = 0.025$. Assuming a 15% attrition rate, a live birth rate of 62%, and that 5% of patients in Cohort A will be excluded from the primary analysis due to exposure to insomnia medications other than QUVIVIQ, a minimum of 204 women will need to be enrolled in Cohort A and 387 in Cohort B1.

STUDY POPULATION

A woman must meet the following criteria to be eligible for enrollment:

Prospective pregnancies:

Inclusion criteria

- Diagnosis of insomnia disorder prior to pregnancy.
- Pregnancy is ongoing and outcome of pregnancy (i.e., pregnancy loss or live birth) is not known.
- One of the following:
 - Woman exposed to QUVIVIQ at any time during the current pregnancy or within 5 half-lives prior to conception.
 - Woman exposed to other, non-orexin receptor antagonist (ORA) medications for insomnia during pregnancy or within 5 half-lives of the respective insomnia medication prior to conception.
 - Woman unexposed to an insomnia medication during pregnancy and within 5 half-lives of any insomnia medication taken prior to conception.

23 October 2023, page 13/90

Doc No D-23.335

Confidential

- Able and willing to consent to the conditions and requirements of the registry. If the patient is a minor, able and willing to consent/assent according to local regulations.
- Agrees to electronically sign the Release of Medical Information Form permitting the study staff to contact her healthcare providers (HCPs) (e.g., primary care provider, insomnia specialist, psychiatrist, obstetrician, nurse midwife) and the infant's HCP (e.g., pediatrician) for medical information.

Exclusion criteria

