5.2.1.1 Eligibility criteria for prospective pregnancies

Inclusion criteria

- Diagnosis of insomnia disorder prior to pregnancy.
- Pregnancy is ongoing and outcome of pregnancy (i.e., pregnancy loss or live birth) is not known.
- One of the following:
 - Woman exposed to QUVIVIQ at any time during the current pregnancy or within 5 half-lives prior to conception.
 - Woman exposed to other, non-ORA medications for insomnia during pregnancy or within 5 half-lives of the respective insomnia medication prior to conception.

Confidential

- Woman unexposed to any insomnia medication during pregnancy and within
 5 half-lives of any insomnia medication taken prior to conception.
- Able and willing to consent to the conditions and requirements of the registry. If the patient is a minor, able and willing to consent/assent according to local regulations.
- Agrees to electronically sign the Release of Medical Information Form permitting the study staff to contact her HCPs (e.g., primary care provider, insomnia specialist, psychiatrist, obstetrician, nurse midwife) and the infant's HCP (e.g., pediatrician) for medical information.

Exclusion criteria

- Exposure to any ORA other than QUVIVIQ (including BELSOMRA® (suvorexant), DAYVIGO® (lemborexant), any ORA newly approved during the study period, or any ORA in pre-market clinical studies) during the current pregnancy or within 5 half-lives of the respective medication prior to conception.
- Woman is currently participating in an interventional study or has taken an investigational product within 3 months prior to conception or during the current pregnancy.

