5.5 Study size

5.5.1 Sample size calculation for the primary outcome

The sample size (i.e., the number of enrolled patients) was calculated to ensure sufficient power to compare the prevalence of major congenital malformations in the infants of women exposed to QUVIVIQ (Cohort A) with infants of women exposed to other non-ORA medications for insomnia (Cohort B1) in the primary analysis using an NI testing approach with a one-sided significance level of $\alpha = 0.025$.

Hypothesis:

```
H_0: P_A- P_{B1} > margin versus H_1: P_A- P_{B1} < margin
```

where

P_A is the probability of major congenital malformations in Cohort A.

P_{B1} is the probability of major congenital malformations in Cohort B1.

The null hypothesis is that P_A is larger than P_{B1} by a margin corresponding to a risk ratio of 3.0:

```
Risk Ratio = (P_{B1} + margin) / P_{B1}
or margin = P_{B1}*Risk Ratio -P_{B1}
```

A general population prevalence of major congenital malformations of 3% among women in Cohort B1 is assumed. The NI margin is 3%*3.0–3%=6%.

Assuming a true difference of 0.15% between P_A and P_{B1} (corresponding to a relative increase of 5% from P_{B1}), sample sizes of 102 pregnancy outcomes in Cohort A and 204 events in Cohort B1 achieve 80.1% power to exclude an increase in risk of more than a risk ratio of 3 in Cohort A compared to Cohort B1. The test statistic used is the one-sided Z-test with a significance level of 2.5%. The proportion for the reference group is $P_{B1} = 3\%$

[see Table 3]. Calculations were made by using nQuery V9.1.1.0, module PTE0U-1 [Machin 1987].

The hypothesis testing will be based on comparing the upper bound of the 97.5% one-sided confidence interval for P_{A^-} P_{B1} with the NI margin. If the upper bound is below the NI margin, then noninferiority of A vs B1 will be concluded.

The following formula was utilized to calculate sample size:

$$Na = \frac{(r+1) * (Z_{1-\beta} + Z_{1-\alpha})^{2} * (\frac{Pa * (1-Pa) + Pb1 * (1-Pb1)}{2})}{r * ((Pa - Pb1) - margin)^{2}}$$

$$Nb1 = r * Na$$

where N_A is the number of pregnancy outcomes required in Cohort A, N_{B1} is the number of pregnancy outcomes required in Cohort B1, r is the allocation ratio (Cohort A: Cohort B1, 1:2 ratio), $Z_{1-\beta}$ and $Z_{1-\alpha}$ are the 80% and 97.5% percentiles of the standard normal distribution, respectively.

Sample size estimates with risk ratios varying from 2.0 to 3.0 and with various observed percentages in Cohort A are presented in Table 3.

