These numbers are further adjusted with a 15% attrition rate (drop-out or missing data), a live birth rate of 62% [FDA 2002], and assuming that 5% of patients in Cohort A will be excluded from the primary analysis due to exposure to insomnia medications other than QUVIVIQ.

The calculation for the number of enrolled patients needed is as follows:

$$Enrolled\ patients = \sum_{i \in A, B1, B2} \frac{Pregnancy\ outcomes\ needed\ for\ each\ group_i}{Overall\ adjustment\ rate\ for\ each\ group_i}$$

For Cohort A the overall adjustment rate is as follows:

 $(1 - drop \ out \ rate \) \cdot (1 - proportion \ of \ pts \ with \ combined \ insomnia \ drugs) \cdot live \ birth \ rate = (1 - 0.15) \cdot (1 - 0.05) \cdot 0.62 = 0.50065.$

For Cohort B1 and B2 the overall adjustment rate is as follows:

$$(1 - drop \ out \ rate) \cdot live \ birth \ rate = (1 - 0.15) \cdot 0.62 = 0.527$$

The total number of enrolled patients needed in each cohort (Cohort A, Cohort B1 and Cohort B2, respectively) is as follows:

Number of enrolled patients =

$$\frac{102 (A)}{0.50065} + \frac{204 (B1)}{0.527} + \frac{102 (B2)}{0.527}$$
$$\approx 204 + 387 + 194 = 785$$

The number of enrolled patients needed depending on risk ratios varying from 2.0 to 3.0 and depending on expected prevalence of major congenital malformation in Cohort A are presented in Table 3.

 Table 3
 Sample size calculation

					nts to be enrolled ohort
Risk ratio	Assumed prevalence in Cohort B1	Expected prevalence of MCM in Cohort A ^a	NI margin corresponding to the risk ratio	Cohort A with 15% attrition rate, 62% live birth rate, and 5% exposure to insomnia medications other than QUVIVIQ	Cohort B1 with 15% attrition rate and 62%live birth rate
3.0	3.0%	3.0%	6%	192 (Pregnancy outcomes needed: 96)	362 (Pregnancy outcomes needed: 191)
3.0	3.0%	3.15%	6%	204 (Pregnancy outcomes needed: 102)	387 (Pregnancy outcomes needed: 204)
3.0	3.0%	3.3%	6%	218 (Pregnancy outcomes needed: 109)	414 (Pregnancy outcomes needed: 218)
2.75	3.0%	3.0%	5.25%	250 (Pregnancy outcomes needed: 125)	472 (Pregnancy outcomes needed: 249)
2.75	3.0%	3.15%	5.25%	268 (Pregnancy outcomes needed: 134)	509 (Pregnancy outcomes needed: 268)
2.75	3.0%	3.3%	5.25%	290 (Pregnancy outcomes needed: 145)	548 (Pregnancy outcomes needed: 289)

Confidential

					nts to be enrolled ohort

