5.7.1.3 Primary analysis

The final primary analysis will be conducted once all data collection is complete, including up to 21 months of follow-up for enrolled patients. Only women with prospective pregnancies (i.e., outcome of the pregnancy is not known at time of enrollment) will be included in the primary analysis.

Confidential

The primary outcome for this study is major congenital malformations in infants. All other outcomes will be classified as secondary.

The primary analysis will use risk ratios (one-sided 97.5% CI) to compare major congenital malformations in infants between Cohort A and Cohort B1 among women with first trimester exposure to their respective insomnia medications. Women exposed to QUVIVIQ who take other medications for insomnia at any time during pregnancy will be excluded from the primary analysis. Women with known teratogen exposure during pregnancy will be included in the primary analysis. Sensitivity analyses will be conducted evaluating timing of exposure. Additional sensitivity analyses will be conducted, including women exposed to QUVIVIQ who were exposed to other insomnia medications, and excluding those with known teratogen exposure [Section 5.7.4.4].

Adjudicated major congenital malformations reported up to 1 year of age by the mother or by an HCP will be included in the primary analysis. Pregnant women who receive any prenatal screening after enrollment (post-enrollment) that provides knowledge of the pregnancy outcome will be included in the primary analysis. Decision criteria with regard to prenatal testing before enrollment (pre-enrollment) will be applied to the study population for inclusion in the primary analysis as follows: pregnant women with pre-enrollment prenatal testing who have not received the test results at the time of enrollment will be included in the primary analysis, while pregnant women who had prenatal testing pre-enrollment where the result is known prior to enrollment will be included or excluded from the primary analysis depending on the result of the test (see Table 5 for pertinent descriptions for inclusion in analyses based on timing and the results of prenatal screening tests).

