5.9.3 Analytic limitations

Enrollment below the targeted sample size of 204 in Cohort A, 387 in Cohort B1, and 194 in Cohort B2 may limit the ability to address multiple strata or subgroups due to low sample size. The power of statistical comparisons to Cohort A of women with insomnia who are not exposed to QUVIVIQ could also be impacted by low enrollment; adjustment for covariates may not be feasible. The comparison of Cohort A to Cohort B will be performed and adjusted to relevant covariates if a sufficient number of outcomes are available. An interim analysis will be conducted at year 5 of the study to evaluate patient enrollment and inform awareness, recruitment, and retention plans as well as inform downstream sample size projections.

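### The enrollment targets of 204 and 387 assume that every woman was exposed in the primary malformation window, but eligibility accepts exposure at any time in pregnancy and section 5.5.1 has no factor for the difference

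*Protocol*

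**What the plan says.** **Who is enrolled.** Protocol section 5.2.1.1 admits to Cohort A a "Woman exposed to QUVIVIQ at any time during the current pregnancy or within 5 half-lives prior to conception". The Cohort B1 criterion has the same breadth: exposure to a non-ORA insomnia drug during pregnancy or within 5 half-lives before conception. Section 5.3.1 assigns cohorts in the same way.

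**Who is in the primary analysis.** Section 5.7.1.3 compares malformations "among women with first trimester exposure to their respective insomnia medications". Sections 5.7.2.1 and 5.7.4.2 and Appendix 4 extend the window back to 5 half-lives before conception. Under either wording, exposure that begins after the first trimester is outside it. The protocol expects such women: section 5.7.1.3 plans exploratory analyses of exposure in another trimester, and the footnote to Table 6 lists second-trimester-only and third-trimester-only exposure.

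**How the targets are built.** Section 5.5.1 needs 102 and 204 outcomes, which it says "achieve 80.1% power to exclude an increase in risk of more than a risk ratio of 3 in Cohort A compared to Cohort B1". It then states: "These numbers are further adjusted with a 15% attrition rate (drop-out or missing data), a live birth rate of 62" percent, and a further 5% deduction in Cohort A for women who also took other insomnia drugs. The resulting rates are 0.50065 (A) and 0.527 (B1).

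**Where timing is mentioned.** The synopsis opens its sizing sentence with "Assuming exposure in the first trimester of pregnancy, a general population prevalence of major congenital malformations of 3% among women in Cohort B1". Section 5.5.1 says only "A general population prevalence of major congenital malformations of 3% among women in Cohort B1 is assumed", without the timing condition. Section 5.9.3 gives the targets as plain enrollment: "Enrollment below the targeted sample size of 204 in Cohort A, 387 in Cohort B1, and 194 in Cohort B2".

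**The concern.** A woman with insomnia who first takes her drug in week 20 or week 30 is eligible, is assigned to Cohort A or B1, and on a plain reading counts toward 204 or 387. She contributes nothing to the primary comparison. Section 5.5.1 accepts that exclusions from the primary analysis belong in the conversion, because it deducts the combined-drug exclusion. It leaves out the other exposure-based restriction, which stands in the same paragraph of section 5.7.1.3.

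At stake is the power of the primary comparison, a safety question tested for non-inferiority. If the targets are read as total enrollment, the registry can reach them with fewer evaluable outcomes than the stated power needs. None of the planned reviews names the count that would show this.

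**Working it through.** **Inputs.** From section 5.5.1: one-sided alpha 0.025; P_B1 = 3%; P_A = 3.15%; margin 6 percentage points; outcomes 102 and 204; attrition 15%; live birth 62%; combined insomnia drugs 5% (A only). From Table 4: live birth 62%, elective or therapeutic termination 18%, fetal death or stillbirth 1.4%, spontaneous abortion 11%. The share f of enrolled women whose exposure falls in the primary window is not in the protocol. It is varied here as an assumption, equal in both cohorts.

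**1. Reproducing the plan's figures.**
- The printed formula gives N_A = 3 × (1.96 + 0.8416)² × 0.0298 / (2 × 0.0585²) ≈ 102.5 and N_B1 ≈ 205.1, against 102 and 204 stated.
- Power = Φ((0.06 − 0.0015)/SE − 1.96). With the size-weighted pooled proportion of 3.05%, SE = √(0.0305 × 0.9695 × (1/102 + 1/204)) = 0.02085 and power is 80.1%, as stated. With the averaged variance of the printed formula it is 79.8%; the difference is immaterial.
- 102 / 0.50065 = 203.7 and 204 / 0.527 = 387.1, against 204 and 387 stated.

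The stated arithmetic is sound.

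**2. Slack.** Run in reverse, 204 × 0.50065 = 102.1 and 387 × 0.527 = 203.9. There is no reserve, so on these factors f below 1 leaves fewer than 102 and 204 outcomes.

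**3. Adding f on the live-birth unit.** Outcomes are 204 × 0.50065 × f and 387 × 0.527 × f. Power uses the pooled form that reproduces 80.1%. Enrollment needed is 102/(0.50065 f) and 204/(0.527 f), rounded up.

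| f (assumed) | Outcomes A / B1 | Power at 204/387 enrolled | Enrollment needed A / B1 |
|---|---|---|---|
| 1.00 | 102 / 204 | 80.1% | 204 / 387 (as stated) |
| 0.95 | 97 / 194 | 78.1% | 215 / 408 |
| 0.90 | 92 / 184 | 75.9% | 227 / 431 |
| 0.80 | 82 / 163 | 70.9% | 255 / 484 |
| 0.70 | 71 / 143 | 65.1% | 292 / 553 |

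If only Cohort A loses women, power is about 77% at f = 0.9 and about 74% at f = 0.8.

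**4. Same calculation on the total-prevalence unit.** Section 5.7.4.2 defines total prevalence over all pregnancies except spontaneous terminations and ectopic or molar pregnancies. Replace 62% by 62% + 18% + 1.4% = 81.4%:

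| f (assumed) | Outcomes A / B1 | Power at 204/387 enrolled |
|---|---|---|
| 0.95 | 127 / 254 | 88% |
| 0.90 | 121 / 241 | 86% |
| 0.80 | 107 / 214 | 82% |
| 0.70 | 94 / 187 | 77% |

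Break-even is f = 0.62/0.814 = 0.76. If only the 11% spontaneous abortions are removed (89% remain), it is 0.62/0.89 = 0.70.

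**The case against.** Four arguments weigh against the point.

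- **The assumption is disclosed.** The synopsis states first-trimester exposure in the sentence that derives 102 and 204, so it is not hidden. Wide eligibility is deliberate, because later-exposed women serve the secondary and exploratory analyses. Both statements are right. But the synopsis condition amounts to f = 1, and nowhere does the protocol say that 204 and 387 count only women with qualifying exposure.
- **The 62% factor may already cover the loss.** On the total-prevalence unit it does, down to about f = 0.70 to 0.76. This stands as a limit on the size of the problem. It does not remove it: section 5.5.1 sizes on live births and claims no such offset, and section 5.7.4.2 also defines a prevalence at birth without saying which of the two is primary.
- **f is probably high.** Insomnia must be diagnosed before pregnancy (5.2.1.1), enrollment is wanted as soon as pregnancy is known (5.2), and providers are asked to refer early (5.4.5). That makes the rows near f = 0.9 more plausible than those near 0.7, but none of these provisions rules out first use later in pregnancy.
- **Interim review allows correction.** Section 5.7.1.1 reassesses the sample size assumptions at year 5, and section 5.5.1 plans re-estimation. Neither names exposure timing.

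A reader might go further and infer that 204 and 387 enrolled will certainly fail to deliver the stated outcomes, or that recruitment closes on reaching them. The documents support neither. The first depends on an unknown f and an unresolved denominator. On the second, the synopsis calls 204 and 387 a minimum, and nothing in the protocol closes enrollment there.

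**Conclusion.** The point holds as an unquantified assumption in the sizing, not as a proven shortfall. The step from outcomes to enrolled women takes the share with qualifying exposure as 100%, while eligibility and the planned later-trimester analyses imply less. The direction is certain on the live-birth unit that section 5.5.1 uses. There the loss is about 2 to 4 points of power at f = 0.95 to 0.9, about 9 points at 0.8 and 15 at 0.7, assuming f equal in both cohorts and all other factors as stated. On the total-prevalence unit, power stays above 80% down to about f = 0.70 to 0.76. It should be fixed; confidence in the omission is high, and in its magnitude only medium.

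**What to change.** In the synopsis, section 5.5.1 and section 5.9.3, do one of two things:

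- define 204 and 387 as counts of women whose exposure falls in the primary malformation window; or
- multiply both adjustment rates by an explicit, stated share (it may differ between A and B1) and restate the power for 204 and 387 enrolled, or restate the enrollment.

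In addition:

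- state which denominator of section 5.7.4.2 the sizing uses, and whether the 62% factor follows from it;
- reconcile the exposure window in section 5.7.1.3 with sections 5.7.2.1 and 5.7.4.2 and Appendix 4;
- report qualifying and total enrollment separately in the annual and year-5 reviews.

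Eligibility does not change, and women exposed only later still contribute to the secondary outcomes. The cost is some wording, possibly one factor, and one line in enrollment tracking. The downside is that the stated power for 204 and 387 total enrolled becomes less favourable, or that recruiting to the qualifying count takes longer.

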The study start date will be the date from which the first data collection of the first patient is recorded in the study database. The end of the study will be the date from which the last data collected from the last patient is recorded in the study database. The study duration for a patient is up to 21 months and the total expected duration of the study is approximately 10 years. If the target sample size has not been achieved within 10 years, an extension of the study duration will be considered. An interim analysis will be performed at 5 years to evaluate enrollment and to revise sample size, if needed.

The study will be conducted in the US, Canada, and countries in the EEA, at a minimum. Depending on the local requirements of other health authorities, patients from other countries may be included in the registry.

There will be at least 1 CC per country that is responsible for overseeing informed consent from all patients and HCP contacts during the study. See Figure 2 for more information on CC data responsibilities.

[figure not shown]
Methods to increase registry awareness and enhance patient recruitment and retention are outlined in Section 5.4.5.

QUVIVIQ® (daridorexant)

Doc No D-23.335

Confidential

Figure 1 Study design schema

^a Time points of patient and HCP contact shown are based on expected intervals and may vary based on real-world observational data collection. Patient will be contacted if the HCP is unresponsive. The preferred source of information will be the HCP.

^b Patients with prospective pregnancies must be enrolled prior to the pregnancy outcome (i.e., pregnancy loss or live birth). Patients with retrospective pregnancies will be enrolled after the pregnancy outcome and the data collection schedule will be modified accordingly.

EDD = estimated delivery date; HCP = healthcare provider.

Confidential

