Risk ratio	Assumed prevalence in Cohort B1	Expected prevalence of MCM in Cohort A ^a	NI margin corresponding to the risk ratio	Cohort A with 15% attrition rate, 62% live birth rate, and 5% exposure to insomnia medications other than OUVIVIO	Cohort B1 with 15% attrition rate and 62%live birth rate
2.50	3.0%	3.0%	4.50%	340 (Pregnancy outcomes needed: 170)	643 (Pregnancy outcomes needed: 339)
2.50	3.0%	3.15%	4.50%	370 (Pregnancy outcomes needed: 185)	698 (Pregnancy outcomes needed: 368)
2.50	3.0%	3.3%	4.50%	401 (Pregnancy outcomes needed: 201)	761 (Pregnancy outcomes needed: 401)
2.25	3.0%	3.0%	3.75%	487 (Pregnancy outcomes needed: 244)	926 (Pregnancy outcomes needed: 488)
2.25	3.0%	3.15%	3.75%	537 (Pregnancy outcomes needed: 269)	1021 (Pregnancy outcomes needed: 538)
2.25	3.0%	3.3%	3.75%	595 (Pregnancy outcomes needed: 298)	1129 (Pregnancy outcomes needed: 595)
2.0	3.0%	3.0%	3.0%	761 (Pregnancy outcomes needed: 381)	1446 (Pregnancy outcomes needed: 762)
2.0	3.0%	3.15%	3.0%	857 (Pregnancy outcomes needed: 429)	1628 (Pregnancy outcomes needed: 858)
2.0	3.0%	3.3%	3.0%	971 (Pregnancy outcomes needed: 486)	1843 (Pregnancy outcomes needed: 971)

^a Expected prevalence in Cohort A is P_A = 1.0, 1.05, 1.10 · P_B, reflecting that the expected prevalence in Cohort A is slightly higher (increase of 0%, 5%, 10%) than the background prevalence in Cohort B.

MCM = major congenital malformation; NI = non-inferiority.

For the secondary analysis (comparison of the prevalence of major congenital malformations in the infants of Cohort A to the infants of Cohort B2), 194 pregnancy

Confidential

outcomes in Cohort B2 (1:1 ratio Cohort A:Cohort B2) would allow 86% power to rule out a difference represented by a risk ratio of 3.5 or higher in major congenital malformations at a significance level of $\alpha = 0.025$.

If the prevalence observed in Cohort A is lower than 3.15% (expected prevalence), there will be greater power to demonstrate that the rate of major congenital malformations in the infants of patients in Cohort A is not larger than in Cohort B1.

Subject recruitment will be evaluated at each interim review. Interim analyses are planned for the 5th year after the first patient enrolls, and annually thereafter [Section 5.1]. This will include a sample size re-estimation examining the observed prevalence and risk ratio of major congenital malformations in Cohort A compared with Cohort B1 and account for patient recruitment rates and enrollment projects.

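### Section 5.5.1 plans yearly interims that re-estimate sample size on the observed A-versus-B1 risk ratio, while the rest of the protocol has one year-5 interim that does not use that comparison

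*Protocol*

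**What the plan says.** **Section 5.5.1.** On timing: "Interim analyses are planned for the 5th year after the first patient enrolls, and annually thereafter", with a pointer to section 5.1. On content: a "sample size re-estimation examining the observed prevalence and risk ratio of major congenital malformations in Cohort A compared with Cohort B1", also taking recruitment into account. The final rule in the same section compares the upper limit of a one-sided 97.5% interval for P_A − P_B1 with a 6-point margin: "If the upper bound is below the NI margin, then noninferiority of A vs B1 will be concluded". No adjustment for adaptation is mentioned.

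**Elsewhere.**
- Section 5.1, the section cited, has one interim at 5 years, to look at enrollment and revise the sample size if needed. It adds: "If the target sample size has not been achieved within 10 years, an extension of the study duration will be considered".
- The synopsis gives one interim, 5 years after first enrollment.
- Table 1 footnote b gives one at year 5, for enrollment and sample size.
- Section 5.7.1.1 gives one at 5 years, for enrollment and sample size assumptions. Its report also describes primary and secondary outcome data.
- Section 5.9.3: "An interim analysis will be conducted at year 5 of the study to evaluate patient enrollment", and to inform recruitment and later sample size projections.
- Section 5.7.3 leaves the number of interims open.
- Section 5.7.1.3 places the final primary analysis after all data collection.

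Only 5.5.1 has annual interims, and only 5.5.1 names the A-versus-B1 risk ratio as a basis for re-estimation.

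**The concern.** There are two linked problems.

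First, the protocol gives two interim schedules, and the cross-reference meant to support the annual one does not. A statistical analysis plan cannot implement both.

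Second, 5.5.1 feeds the quantity under test into the choice of sample size. The planned 2.5% error and 80.1% power belong to a fixed design. If the number of outcomes depends on the interim A-versus-B1 result and the final bound is the ordinary one, the stated error rate no longer applies. The error at stake is concluding that a tripled malformation risk has been excluded when it has not. With a primary outcome at about 3%, the interim risk ratio also rests on very few cases, so it is a poor guide to sample size even apart from error control.

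**Working it through.** **Inputs (5.5.1 and 5.5.1 Table 3).** One-sided α = 0.025; power 80%; P_B1 = 3%; P_A = 3.15%; margin = 3% × 3.0 − 3% = 6 points; r = 2; planned outcomes 102 in A and 204 in B1.

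**1. The plan's own figure.** The protocol's formula is

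N_A = (r+1)(z_0.80 + z_0.975)² × [P_A(1−P_A) + P_B1(1−P_B1)]/2 ÷ [r(P_A − P_B1 − margin)²]

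= 3 × 7.849 × 0.029804 ÷ [2 × (0.0015 − 0.06)²] = 102.5.

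N_B1 = 205.1, and power at 102/204 is 79.8% against the stated 80.1%. The figure reproduces as a fixed design, with no allowance for adaptation.

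**2. Error by normal approximation.** The protocol gives no re-estimation rule, cap or information fraction, so these are assumptions: one look at half information; N re-set to give 80% power at the observed effect; N may only rise; unadjusted final test. Simulated at the non-inferiority boundary:

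| Cap on N | One-sided error (nominal 2.5%) |
|---|---|
| 1.5 × | 2.8% |
| 2 × | 3.0% |
| 3 × | 3.2% |

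Repeating the re-estimation at 50, 60, 70, 80 and 90% information gives 2.8%, 3.0% and 3.3%, a change of about 0.1 point at most. If N may also fall, the range is 3.0–3.7%.

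**3. Binomial check.** At P_A = 9% and P_B1 = 3%, with the unpooled (Wald) interval:
- Fixed 102/204: about 5.1%, already twice nominal.
- Re-estimation at 51/102, increase only, caps 1.5–3: 5.1–5.3% when half a case is added to the interim counts, 5.3–5.5% when raw counts are used.
- Fixed designs at 1.5, 2 and 3 times N: about 4.5%, 4.1% and 3.7%.

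Re-estimation therefore adds about 0 to 0.4 points to the plan's own fixed test. It also forgoes the improvement that a larger fixed sample would bring.

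**4. Stability of the basis.** Assume 51 outcomes in A and 102 in B1, with 3 B1 cases (102 × 3% = 3.06). Put the observed proportions into the protocol's formula with the margin held at 6 points. For one Cohort A case, P_A = 1/51 = 0.0196 and P_B1 = 3/102 = 0.0294, so N_A = 3 × 7.849 × 0.02388 ÷ [2 × (−0.0698)²] = 58. In the same way:

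| Cohort A cases | Probability if P_A = 3.15% | Required N_A |
|---|---|---|
| 0 | 20% | 21 |
| 1 | 32% | 58 |
| 2 | 26% | 155 |
| 3 | 14% | 528 |
| 4 | 5% | about 4,900 |

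Expected Cohort A cases are 51 × 0.0315 = 1.6. The standard error of ln RR is about √(1/1.6 + 1/3.06) = 0.98, so the 95% interval for the risk ratio runs roughly 6.8-fold either side. One case more or less moves the target by a factor of nearly three or more, under the plan's own assumptions.

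**The case against.** **Where the re-estimation rule would sit.** Rules, caps and test adjustments usually belong in the statistical analysis plan, which is not shown and may contain them. This stands: their absence from the protocol is not counted here. The conflicting schedules and the stated risk-ratio basis are protocol text and remain.

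**How far 5.5.1 commits the sponsor.** It says only that re-estimation will examine the risk ratio and account for recruitment, not that N follows the observed effect. That is fair, and it is why the error figures depend on assumed rules. But a re-estimation that examines the comparative effect leaves that route open.

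**Size.** The binomial increment over the fixed test is at most about 0.4 points, and annual repetition adds almost nothing. Both are correct. Half accrual at the interim is also an assumption; section 5.4.5.2 calls uptake unpredictable, and later looks would hold more data.

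**Stronger readings a reader might infer.** One is that the other sections confine the interim to enrollment. They do not: 5.1 and Table 1 footnote b allow sample size revision, and 5.7.1.1 reports outcome data. Another is that non-inferiority is tested at every annual look. No interim test or early stopping is stated, and 5.7.1.3 puts the final primary analysis after data collection. A third is that the study may be extended until non-inferiority is reached. The synopsis and 5.1 tie extension to missing the target sample size, not to the result.

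**Conclusion.** The point holds in a limited form and should be fixed. Section 5.5.1 contradicts the section it cites and four other places on the number of interims, and it alone bases re-estimation on the comparative effect. That contradiction needs no assumptions.

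The error inflation is modest: about 2.8–3.3% against 2.5% by normal approximation, given one or more increase-only looks from half information with caps of 1.5–3 times. On the binomial scale the test stays at about 5.1–5.5% against 5.1% for the fixed design. Confidence in these sizes is limited because the rule is assumed. The instability is the stronger practical argument: at an assumed 51/102 outcomes, the interim comparison could put the target below what has already accrued or far beyond what a registry of this size could reach.

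**What to change.** 1. State one schedule in the synopsis, Table 1, 5.1, 5.5.1, 5.7.1.1, 5.7.3 and 5.9.3: a single re-estimation at year 5, with later annual reports descriptive. Yearly safety reporting under 5.7.4.4 is unaffected.
2. In 5.5.1, delete the A-versus-B1 risk ratio as an input to re-estimation. Base re-estimation and any extension on accrual, attrition, live-birth fraction and malformation prevalence not compared between cohorts, for example pooled prevalence. Note there that the margin rests on a B1 assumption ("A general population prevalence of major congenital malformations of 3% among women in Cohort B1 is assumed"), which pooled prevalence reflects only in part.
3. If comparative re-estimation is kept, pre-specify its rule, its cap and a final test that preserves the one-sided 2.5% level.

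The cost is protocol wording, best settled before the year-5 data are seen. The downside is that N can no longer respond to the interim effect, which at that stage carries very little information. The change does not by itself keep comparative data from the sponsor, because safety data are still analyzed by cohort.
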